518 dynamics and biological pathways within the human host that are affected by
519 military-relevant stress and are associated with physical and cognitive performance,
520 and identify novel markers of physiological stress.

521

522 **B5. RESEARCH PLAN**

523

524 **B5.1 Research Design**

525

526 This randomized cross-over study will consist of four sequential phases (SUSOPS 1, Recovery
527 1, SUSOPS 2, and Recovery 2).

528

529 **B5.2 Research Subjects/Population(s)**

530

531 **B5.2.1 Subject Population(s)**

532

533 Healthy, recreationally-active adult men, who are active duty military, will be recruited to
534 participate in this study. Male subjects were chosen because of known sex differences in
535 iron status and absorption and differences in their response to exercise, including the IL-
536 6 response to exercise [62, 63]. Pending the outcomes from this study, future, more
537 targeted studies will be designed to address potential sex-based differences in
538 physiological responses to SUSOPS.

539

540 **B5.2.2 Number of Subjects, Records, and/or Specimens**

541

542 This protocol requires 15 subjects complete testing to provide 80% power to detect
543 significant differences in circulating hepcidin responses between SUSOPS 1 and
544 SUSOPS 2. Up to 60 subjects will be enrolled to account for attrition and screening

545 failures in order to get complete data on 15 subjects. See section B5.8.1 for details on
546 sample size calculations.
547

548 **B5.2.3 Inclusion Criteria**

- 549 • Men who are active duty military, aged 18 – 39 years
- 550 • Weight stable in the past 2 months (\pm 2.27 kg)
- 551 • Healthy without evidence of chronic illness, medication use, or musculoskeletal injury
- 552 as determined by the USARIEM Office of Medical Support and Oversight (OMSO)
- 553 • Recreationally active (2-4 days per week aerobic and/or resistance exercise)
- 554 • Refrain from taking any pain-relievers (e.g., acetaminophen), nonsteroidal anti-
- 555 inflammatory drugs (e.g., aspirin, Advil®, Aleve®, Naprosyn®), or any other aspirin-
- 556 containing product for 10 days before starting and at least 5 days after completing
- 557 the study
- 558 • Refrain from the use of alcohol and nicotine for the duration of the study
- 559 • Willing to refrain from alcohol, smoking any nicotine product (includes e-cigarettes),
- 560 vaping, chewing tobacco, caffeine, and dietary supplement use, and from

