976 [<http://www.medtronic.com/covidien/products/motility-testing/smartpill-motility-testing-system#>].
977 The device continuously measures gastrointestinal pH, core temperature, gastrointestinal
978 pressure, and gastrointestinal transit time for up to 5 d, and can isolate transit through the
979 stomach, small bowel, and colon [80]. One sterile SmartPill will be ingested immediately after
980 breakfast on days -1, 4, and 14 under staff supervision. The pill is easy to swallow and
981 volunteers will be given ample instruction. Elimination of the pill from the gastrointestinal tract
982 will be confirmed by a temperature decrease when the capsule passes from the body into toilet
983 water. If a pill stops transmitting before being eliminated from the body, a new pill may be
984 administered and fecal sample collections will be used to visually search for and confirm exit of
985 the pill that is no longer transmitting. We expect most volunteers will pass the capsule within
986 24-48 hr based on data from Rao et al. [81] who reported median [IQR] whole gut transit time of
987 30 hr [22-46 hr] in 81 healthy adults. Volunteers will wear a bracelet indicating the pill is inside
988 of them until elimination from the body is confirmed by study staff. Transit time will be used in
989 interpretation of the gut microbiota, gastrointestinal permeability, and appetite results as
990 changes in transit time could impact all of these measures. A subset of volunteers will be
991 recruited randomly to participate in this procedure using a random number generator. If any
992 volunteer who is randomly selected reports difficulty swallowing large pills or any other
993 contraindication (see below), they will be replaced with a randomly selected alternate.
994

994 Contraindications:

- 995 • History of gastric bezoar
- 996 • Swallowing disorders; severe dysphagia to food or pills
- 997 • Suspected or known strictures, fistulas, or physiological/mechanical GI obstruction
- 998 • Implanted or portable electro-mechanical medical devices
- 999 • Using proton pump inhibitors
- 1000 • Cannot stop use of the following medications within 48hr of procedure: histamine
1001 blockers, GI motility-altering medications, antiemetics & 5HT3 antagonists, macrolides,
1002 anticholinergics, 5HT4 partial agonists, antacids

1003
1004 **Gastrointestinal health log**
1005 Frequency of bowel movements and subjective ratings of gastrointestinal symptoms (e.g.,

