1426
1427
1428
1429
1430
1431
1432
1433
1434

Samples sizes (n) calculated using <https://glimmpse.samplesizeshop.org/>. r, correlation between phases (P) and over time within each phase (T); R, recovery; S, SUSOPS; SD, standard deviation. Values based on those measured during USARIEM protocol H10-09 [109]].

Using data obtained using the SmartPill in a study of 73 healthy adults we estimate that mean gastrointestinal transit time at baseline will be 29.5 hr (SD = 11.0 hr) [107]. Horner et al. [108] reported a large effect size of 1.0 in a meta-analysis of high-quality studies that measured changes in orocecal transit time in response to exercise. A similar effect size was reported by Corvilain et al. [109] who measured gastric emptying in healthy

1435 adults before and after a 4-d fast. Using these data and a conservative correlation
1436 between repeated measurements of $r = 0.50$ (Diaz-Tartera et al. [107] reported $r = 0.99$),
1437 we estimate that $n = 8$ participants will provide $>80\%$ power to detect a main effect of
1438 condition at $\alpha = 0.05$. This sample size will also provide $>80\%$ power to detect a
1439 main effect should the effect size be medium (effect size = 0.5) and the correlation
1440 between repeated measurements ($r = 0.90$) more similar to that reported by Diaz-Tartera
1441 et al. [107]. We will enroll at least $n = 9$ in this procedure to ensure complete data is
1442 collected on 8 participants. Due to equipment availability, $n = 9$ is also the maximum
1443 number of participants we can measure simultaneously. However, should multiple
1444 iterations be needed to complete data collection, we will enroll up to $n = 9$ participants
1445 during each iteration. Although $n = 8$ is sufficient to detect a main effect of condition,
1446 enrolling more than $n = 9$ will provide greater power to detect associations between
1447 changes in gastrointestinal transit time and changes in gut microbiota composition,
1448 intestinal permeability, and appetite-related outcomes.

1449
1450 Next Generation Sequencing (maximum 200 million pair-end reads) of blood mRNA
1451 samples from 15 participants will yield 60% statistical power to detect a true difference in
1452 expression of at least 1.5 fold with group coefficient variation 0.4, and a conservative
1453 false discovery rate of 0.05 using moderated t -tests and with transcriptome coverage of
1454 9 over reference human genome with sequence length of 150 base pairs. Note, a more

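### The SmartPill subset is drawn at random with no stated link to diet sequence, and the transit model may drop its period contrast; a within-sequence draw and a retained term are a cheap improvement

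*Combined protocol and SAP*

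**What the plan says.** **Design.** Section B5.1: "This randomized cross-over study will consist of four sequential phases". Section B5.3 (Experimental Design) has each man switch diet for the second SUSOPS. No allocation ratio, blocking or balance rule for the sequence is given.

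**Selection.** Section B5.3 (Gastrointestinal transit time) says a subset will be "recruited randomly to participate in this procedure using a random number generator". If a selected man has trouble with large pills or another contraindication, "they will be replaced with a randomly selected alternate" applies. Neither sentence mentions diet sequence. Capsules are taken on days -1, 4 and 14, that is, once before the SUSOPS and once in each.

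**Numbers.** Section B5.2.2: "This protocol requires 15 subjects complete testing to provide 80% power to detect" the hepcidin difference. Section B5.8.1 sets at least nine men for the SmartPill, to secure eight with complete data. It gives nine as the most that can be measured at one time, and adds that should several "iterations be needed to complete data collection, we will enroll up to" nine in each.

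**Model.** Section B5.8.2 (Secondary Objectives) analyses transit time with a linear mixed model, with subject random and phase fixed. A group (sequence) effect and a group-by-phase interaction enter the initial model as a carry-over check. They are taken out if they do not contribute significantly to the fit.

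**The concern.** Each man gives one transit time under BAL and one under NEG BAL, one in the first SUSOPS and one in the second. His BAL minus NEG BAL difference is therefore also a difference between first and second exposure. Being his own control does not remove that. It cancels only if the two sequences are equally represented, or if the model adjusts for it.

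For the BAL versus NEG BAL comparison, the group-by-phase term is the period contrast. Dropping it on a non-significant test removes the adjustment, and in about nine men that test has little power. So an uneven subset either leaves part of any period effect (adaptation or training, for example) in the diet estimate, or costs precision if the term is kept.

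Transit time appears in secondary objectives 2 and 3, and section B5.3 intends to use it when interpreting the microbiota, permeability and appetite results.

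**Working it through.** **1. The plan's own figure.** Section B5.8.1 gives eight men for more than 80% power, with effect size 1.0, correlation 0.50 and alpha 0.05. The standardised within-man difference is 1.0/√(2(1 − 0.50)) = 1.0. The normal approximation, two-sided, gives n = (1.960 + 0.842)² = 7.85, so 8, with power 80.7%. The figure reproduces on that basis. A two-sided paired t-test at n = 8 gives 68.1%, so there is little precision to spare. The plan states no figure for sequence imbalance.

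**2. Chance of an uneven draw.** Assumptions: nine men drawn from a pool of 15, split 8:7 by sequence. Let k be the number drawn from the sequence of eight. Then P(k) = C(8,k)·C(7,9−k)/C(15,9), with C(15,9) = 5005.

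| k | 2 | 3 | 4 | 5 | 6 | 7 | 8 |
|---|---|---|---|---|---|---|---|
| ways | 28 | 392 | 1470 | 1960 | 980 | 168 | 7 |

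- 6:3 either way: (392 + 980)/5005 = 27.4%
- 7:2 or worse: (28 + 168 + 7)/5005 = 4.1%
- 6:3 or worse: 1575/5005 = 31.5%

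The same calculation under other assumptions, still drawing nine:

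| Pool and split | P(6:3 or worse) |
|---|---|
| 9 men, 5:4 | 0% |
| 12 men, 6:6 | 18.2% |
| 15 men, 8:7 | 31.5% |
| 18 men, 9:9 | 34.7% |
| 15 men, 9:6 | 47.1% |
| Sequence by unrestricted coin toss | 50.8% |
| 15 men, 10:5 | 70.6% |

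**3. If the sequence terms are dropped.** The diet estimate is then the plain mean of the within-man differences. A period effect enters with opposite sign in the two sequences, so the estimate carries (n1 − n2)/n of it: 1/9 at 5:4, 3/9 at 6:3 and 5/9 at 7:2.

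Illustration: take the plan's SD of 11.0 hr and r = 0.50, and assume a period effect of half an SD, 5.5 hr. The documents give no period effect, so this size is an assumption. The bias is 5.5/9 = 0.6 hr at 5:4, 5.5/3 = 1.8 hr at 6:3, and 5.5 × 5/9 = 3.1 hr at 7:2. At 6:3 the standard error of the period estimate is (11/2)·√(1/6 + 1/3) = 3.89 hr. The power to detect 5.5 hr is then about 23% (two-sided t, 7 df), so the term would usually be removed.

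**4. If the terms are kept.** The variance of the period-adjusted diet estimate is proportional to 1/n1 + 1/n2. Relative to 5:4:

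- 6:3: (1/5 + 1/4)/(1/6 + 1/3) = 0.90, a standard error 5.4% larger
- 7:2: (1/5 + 1/4)/(1/7 + 1/2) = 0.70

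With effect size 1.0 and r = 0.50, power at n = 9 is 72.5% at 5:4 and 68.1% at 6:3.

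**5. After the change.** Drawing five and four within sequence makes the chance of a 6:3 or worse split at selection 0%, provided each sequence has enough eligible men. The 5:4 split is the best possible with nine.

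**The case against.** Several points on the other side stand.

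- A reader might infer that the plan carries a 31% risk of imbalance. It does not state enough for that: the 8:7 split and the pool of 15 are assumptions, and the figure moves from 0% to 71% with them.
- A reader might infer a fixed comparison of nine men. Section B5.8.1 makes nine a minimum and a per-iteration cap. A cohort of nine or fewer needs no draw for capacity, and two iterations could cover all 15 men.
- A reader might infer that order is never adjusted for. The initial transit model does contain the right term. What leaves the exposure is the rule that removes it.
- That the draw disregards sequence is read from silence. The protocol neither stratifies nor says that it will not.
- The likely loss is small. Most of the 31.5% is 6:3, which keeps 90% efficiency when period is adjusted for.
- Balance would not remove differential carry-over, which biases the diet contrast even with equal sequences. It also does nothing for the baseline comparison, since day -1 always comes first.

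Random selection for a secondary measure is defensible. None of this argues for leaving balance to chance when a draw is needed anyway, or for letting a weak test decide whether period is adjusted for.

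**Conclusion.** The point holds in a limited, conditional form. As written, the draw and the choice of alternates do not protect balance between sequences, and the model may discard the term that would compensate. Under the 8:7 and 15-man assumption the chance of 6:3 or worse is 31.5%. The consequence at 6:3 is either one third of any period effect left in the diet estimate, or about 10% of efficiency lost; at 7:2 it is five ninths, or about 30%. Whether a period effect on transit time exists is not known from the documents. This is a cheap improvement to a secondary comparison. It is not a flaw that invalidates it, and it does not bear on the primary outcomes.

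**What to change.** In section B5.3, state that in any iteration where not all men can be measured, the SmartPill subset is drawn within diet sequence as evenly as possible (five and four when nine are taken), and that an alternate comes from the same sequence as the man he replaces.

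In section B5.8.2, keep the group-by-phase (period) term in the transit model whatever its p-value, and report the BAL versus NEG BAL difference as the equally weighted average over the two sequences.

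**Cost.** No extra men, capsules or visits. Sequence must be assigned before the draw, and the draw must precede the day -1 capsule; the documents do not say when sequence is assigned, so this may change the order of procedures. The period contrast uses one degree of freedom. Balance is guaranteed only at selection, and the plan itself allows for losing one man of nine.

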 604 and be provided a 48 h carbohydrate refeeding diet on days 1 and 2 to restore muscle glycogen
 605 content pre-SUSOPS (**Figure 3**). On day 2, following an ≥ 8 h fast (0000 h), volunteers will
 606 undergo the first of three fractional iron absorption studies (Iron
 607 Study 1), during which time volunteers will ingest a stable isotopically labeled iron ($^{54}\text{FeSO}_4$)
 608 drink followed by serial blood draws over the next 6 h. A fasting blood draw and percutaneous

609 muscle biopsy of the vastus lateralis will be collected on the morning of day 3. Volunteers will
610 also complete approximately 3-4 mood/cognitive-performance familiarization sessions and 1
611 baseline session before the SUSOPS testing period. Immediately thereafter, volunteers will
612 complete a 72-h SUSOPS, and will be provided either sufficient food (combat rations) to
613 maintain energy balance within $\pm 10\%$ of estimated total daily energy expenditure (SUSOPS
614 BAL) or only enough food to match 45% of total daily energy expenditure to elicit severe
615 negative energy balance (SUSOPS NEG BAL). Volunteers will reside at the Doriot Climatic
616 Chambers during the SUSOPS beginning the evening of days 1 and 11 (volunteers will be
617 provided standardized meals), and ending after final data collection on days 6 and 16.
618 Throughout these periods, volunteers will wear the USARIEM Vigilance Monitoring System, the
619 Fatigue Science Readiband™ actigraph, Philips Respironics Actiwatch® Spectrum Plus, or
620 equivalent device on their non-dominant wrist. The activities performed will be comprised of
621 load carriage and unloaded steady-state exercise and Warfighter operational tasks (e.g., 15 m
622 timed casualty evacuation drag of a 123 kg dummy, move under fire, prepare fighting positions)
623 to increase total daily energy expenditures. Physical performance will be assessed before and
624 after each SUSOPS. Mood, cognitive performance and overall vigilance will also be assessed.
625 Sleep will be restricted to four hours per night during SUSOPS to mimic recent field studies. On
626 day 6, immediately following the final exercise bout and 8 h after dinner on day 5, a second
627 muscle biopsy will be collected (alternate leg from biopsy one) and volunteers will undergo Iron
628 Study 2 ($^{57}\text{FeSO}_4$). Days 7-12 will serve as a recovery period from SUSOPS 1 (Recovery 1).

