629 Fasted blood draws will be collected on days 7-9 during Recovery 1, and a second baseline
630 mood/cognitive test session will occur during Recovery 1. Starting on day 11, volunteers will
631 complete a second glycogen normalization and 48 h carbohydrate refeeding protocol. On day
632 13, following an overnight fast, a blood draw and a third muscle biopsy (alternate leg from
633 biopsy two) will be collected. Immediately thereafter, volunteers will complete the second 72 h
634 SUSOPS. All testing, planned activity, and sleep restrictions will be the same as described for
635 SUSOPS I; however, volunteers will switch to either SUSOPS BAL or SUSOPS NEG BAL. Iron
636 Study 3 ($^{58}\text{FeSO}_4$) and the fourth and final muscle biopsy (alternate leg from biopsy three) will
637 occur on day 16 immediately following the final exercise bout and 8 h after dinner on day 15.
638 Days 17-22 will serve as Recovery 2 (7 d post-SUSOPS recovery blood draw will be collected on
639 day 22 to match the 7 d recovery from SUSOPS 1) Diet records will be recorded on days 6-8,
640 and 16-18.

641

642 **SUSOPS BAL and SUSOPS NEG BAL**

643 The SUSOPS will be comprised of a variety of Warfighter tasks, designed to elicit high energy
644 expenditures, muscle damage and fatigue, sleep deprivation, and decrements in physical and
645 cognitive performance as well as self-reported mood status. Most importantly, the SUSOPS will
646 be designed to elicit a marked inflammatory response. Physical activity/exercise will be
647 prescribed at levels to expend ~ 5000 - 6000 total kcal/d using the ACSM metabolic equations for
648 steady-state exercise [64] and the compendium of metabolic equivalents for physical activities
649 [65]. Total daily energy expenditure estimates will be consistent with our recent reports in
650 Norwegian Soldiers and matched between SUSOPS BAL and NEG BAL [55, 66]. Combat
651 rations (Meal Ready-to-Eat) will serve as the underlying diet during SUSOPS BAL and NEG
652 BAL (refer to SUSOPS Diet Intervention section for details). Low-to-moderate intensity (30 - 65%
653 $\text{VO}_{2\text{peak}}$) steady-state endurance-type exercise will be the primary exercise modality.
654 Volunteers will perform three prolonged steady-state exercise bouts per day. All three exercise
655 sessions will be conducted outdoors on Natick Soldier Systems Center grounds (NSSC fitness
656 trail). Two of the three exercise bouts will be ~ 60 - 180 -min load carriage exercise sessions,

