657 whereas the third will be unloaded. The total distance covered will be dictated by individual
658 exercise prescriptions, and the load carried will be ~ 32 kg [comprised of the basic uniform (~ 5.3

659 kg), weapon and tactical equipment (~11.2 kg), and rucksack (~15 kg)]. The loads carried are
660 consistent with infantry occupation standards. Volunteers will be permitted to consume water ad
661 libitum throughout each exercise trial to maintain hydration. During the remainder of each day,
662 volunteers will perform a number of Warfighter tasks [e.g., 15 m timed casualty evacuation drag
663 of a 123 kg dummy, move under fire (15, 6.6 m rushes with weapon and full combat load (32 kg)
664 for time, with 5 secs between rushes), prepare fighting positions (move 16, 18 kg sandbags 10
665 m while wearing full combat load minus a weapon (~26.5 kg)]. The Warfighter task measures
666 will be performed daily to increase energy expenditure by simulating some operational tasks.
667 Volunteers will perform at least two familiarization trials of each task to reduce injury risk during
668 the pre-study baseline period. Mood, cognitive, and vigilance will also be assessed. Self-
669 reported mood and cognitive performance will be assessed twice per SUSOPS day in addition
670 to the sessions performed prior to SUSOPS 1 during the baseline testing phase of the protocol
671 and the session performed during Recovery 1. Vigilance testing using the USARIEM Vigilance
672 Monitoring System will only be active during specific intervals of wake time. Sleep will be
673 restricted to 4 h per day to be consistent with previous USARIEM SUSOPS studies beginning
674 the evening of days 3 and 13(i.e., volunteers will not be permitted to sleep until 0100 the
675 morning of days 4 and 14) [67].

676

677 **Warfighter Tasks**

678 *Move under Fire:* During this task, volunteers will wear an approximately 32 kg fighting load
679 [comprised of the basic uniform (~5.3 kg), weapon and tactical equipment (~11.2 kg), and
680 rucksack (~15 kg)]. They will begin the task in the prone position. Upon command, volunteers
681 will sprint approximately 6 m to a marker and assume the predetermined position for that marker
682 (either the kneeling or prone position). They will remain in this position for approximately 5
683 seconds. Upon signal, volunteers will get up and sprint approximately 5 to 8 m to the next

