1006 flatulence, constipation, loose stool) will be assessed during study days -1 (may be adjusted \pm 2d if
1007 needed), 3, 6, 13, and 16, using modified versions of the Irritable Bowel Syndrome-Symptom

1008 Severity Score Questionnaire [82] and the Gastrointestinal Quality of Life Index [83] (see
1009 “Gastrointestinal Health Log”). Both questionnaires are publicly available and take <5min to
1010 complete.

1011
1012 **Assessment of mucosal immunity**

1013 Secretory IgA will be assessed from saliva samples at baseline and each morning of SUSOPS
1014 to evaluate mucosal immunity. Saliva samples will be collected using the non-invasive
1015 commercially-available Salimetrics polyester Oral Swab (SOS) technology (Salimetrics, CA,
1016 USA). Subjects will be asked to place one SOS under their tongue for 3 minutes before
1017 returning it to the provided vial. Participants will then place a second SOS under their tongue
1018 until the swab is saturated with saliva. This sampling technique will enable us to obtain the
1019 required amount of saliva to determine sIgA concentration and the salivary flow rate at each
1020 time point. Salivary sIgA is a well-documented biomarker of mucosal innate immunity, used to
1021 predict upper respiratory tract infections and to study the influence of stress and dehydration on
1022 immune function [84-86]. The collected saliva will be stored at -80°C until analysis. Saliva
1023 osmolality will be determined using a freezing point depression osmometer, and samples will be
1024 analyzed simultaneously for sIgA concentration using a commercially-available ELISA.

1025
1026 **Self-Reported Mood, Cognitive Performance, and Vigilance Assessments**

1027 Several mood and cognitive performance assessment sessions will be conducted during the pre-
1028 SUSOPS period of testing so that volunteers become familiar with the test battery and their
1029 performance is stable. The last of these sessions will serve as the baseline data for statistical
1030 analyses. During the simulated SUSOPS periods, a morning and evening mood/cognitive test
1031 session will be conducted on each day. Ambulatory vigilance will be assessed via the wrist-worn
1032 USARIEM Vigilance Monitoring System. The Fatigue Science Readiband™ actigraph, Philips
1033 Respironics Actiwatch® Spectrum Plus, or an equivalent device will record sleep data at night and
1034 daytime motor activity. (see “POMS” and “EVAR” documents).

1035

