1455 liberal false discovery rate (e.g., 0.20) may be used to reduce type 2 error rates and
1456 increase power. For microbiome analysis, shotgun sequencing (maximum 50 million
1457 pair end reads) of 15 participants will achieve $\geq 69\%$ power to detect a true difference in
1458 relative abundance of at least 1.5 fold with group coefficient variation 1.3, and false
1459 discovery rate of 0.05. Again, a more liberal false discovery rate (e.g., 0.20) may be
1460 used to reduce type 2 error rates and increase power. Power calculations were
1461 conducted using pairwise distances and PERMANOVA power with respect to effect size.
1462 However, power will be enhanced by correlating the blood mRNA data with other omics
1463 readouts derived from saliva (microRNA-seq, metabolomics and microbiome) and blood
1464 (targeted microRNA and metabolomics), and by temporal sample collection. As such,
1465 we expect that 15 participants will provide adequate power to detect differences in blood
1466 mRNA expression, and gut microbiome community and genome composition between
1467 study phases, and correlations between these parameters and other –omics readouts.

1468 **B5.8.2 Data analysis**

1469
1470
1471 Statistical analyses will be conducted using either SPSS (IBM Corp. Armonk, NY), SAS
1472 9.3 (SAS Institute Inc., Cary, NC), or equivalent. Common descriptive statistics will be
1473 used to describe volunteer characteristics. Shapiro-Wilk tests will be used to determine
1474 normality of data, and transformations will be applied as appropriate to ensure model
1475 assumptions are met. Correlation and multiple regression will be used to evaluate
1476 relationships between study outcomes.

1477 **Primary Objectives**

1478
1479 Linear mixed models will be used to determine main effects of phase (SUSOPS BAL and
1480 SUSOPS NEG BAL), time within phase, and their interaction on inflammation, iron
1481 absorption, mood/cognitive, and measures of muscle, nutritional, and metabolic
1482 homeostasis. If phase by time interactions are observed, a Bonferroni correction will be
1483 applied for multiple comparisons. Statistical significance will be set at $P < 0.05$. To test
1484 for carryover effects a main effect of group (SUSOPS BAL first, SUSOPS NEG BAL first)

1485 and a group-by-phase interaction will be included in initial models. These terms will be
1486 removed if they do not significantly contribute to the overall fit of the model. When

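### The computer mood/cognitive battery has one baseline session before each SUSOPS but is run morning and evening during it, so the before-versus-SUSOPS comparison can absorb ordinary diurnal change

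*Combined protocol and SAP*

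**What the plan says.** **Baseline.** B5.3, Experimental Design, says volunteers will "also complete approximately 3-4 mood/cognitive-performance familiarization sessions and 1" baseline session before SUSOPS. B5.3, Self-Reported Mood, Cognitive Performance, and Vigilance Assessments, makes that final session the analysis baseline: "The last of these sessions will serve as the baseline data for statistical" analyses. Experimental Design adds a second baseline: "mood/cognitive test session will occur during Recovery 1". No clock time is given for either session.

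**During SUSOPS.** The same assessment section schedules two sessions a day: "During the simulated SUSOPS periods, a morning and evening mood/cognitive test" session on each day. Testing is the same in both SUSOPS periods.

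**Model.** B5.8.2, Primary Objectives, covers mood/cognitive outcomes with linear mixed models in phase (SUSOPS BAL and "SUSOPS NEG BAL), time within phase, and their interaction on inflammation, iron" absorption and other outcomes. It does not say whether the levels of time are sessions, days or daily means, and it names no time-of-day factor.

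**Hypothesis.** Secondary hypothesis 4 in B4 has two parts: SUSOPS itself worsens mood and cognition, and negative energy balance makes this worse.

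**The concern.** A single session happens at one time of day. If it is in the morning, the evening SUSOPS sessions have no clock-matched reference, and the reverse holds for an evening baseline. Either way, half of the SUSOPS sessions are compared with a baseline from another part of the day.

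This matters for the first part of hypothesis 4. The study has no non-SUSOPS control period, so the baseline is the only reference for what SUSOPS does to mood and cognition. Any ordinary morning-evening difference in reaction time, fatigue or vigor goes straight into that comparison. It can exaggerate or hide a decrement, depending on the measure and on when baseline was taken. A baseline at the missing time of day cannot be recovered by analysis afterwards.

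The protocol controls clock time elsewhere. The day -1 appetite scales are timed to match the SUSOPS exercise sessions, and a separate draw on iron-study mornings keeps other blood markers at the usual hour. The battery has no such rule.

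**Working it through.** The documents give no power calculation, SD, correlation or diurnal difference for any mood or cognitive measure, so there is no stated figure to reproduce. The size has to be explored under assumptions.

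**Inputs from the documents.** n = 15 (B5.2.2); alpha 0.05 (B5.8.2; two-sided assumed); one baseline session per period; two sessions a day over a 72 h SUSOPS, that is 3 × 2 = 6 sessions.

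**Assumptions.** No true SUSOPS or diet effect; a morning-evening shift d of 0.2, 0.3 or 0.4 SD; equal correlation r between any two sessions of one man, 0.7 with a range of 0.5 to 0.8; baseline in the morning.

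**1. Main time test, time coded by session, one phase.** The seven means are (0, 0, d, 0, d, 0, d), with mean 3d/7. Their sum of squares is 3d² − 9d²/7 = 12d²/7. The noncentrality is λ = 15 × (12d²/7)/(1 − r), with 6 and 84 degrees of freedom. At r = 0.7 this gives λ = 3.43, 7.71 and 13.71. A simulation at d = 0.3 gave 50% against 48% from the formula.

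**2. Pooled contrast, mean of six sessions minus baseline.** The bias is d/2. The SD of the difference is √[(1 − r)(1 + 1/6)], which is √(0.3 × 7/6) = 0.592 at r = 0.7. The noncentrality is (d/2)√15/0.592 = 0.65, 0.98 and 1.31, on 14 degrees of freedom.

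False-positive rates:

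| Test | r | d = 0.2 | d = 0.3 | d = 0.4 |
|---|---|---|---|---|
| Main time test | 0.5 | 14% | 29% | 51% |
| Main time test | 0.7 | 22% | 48% | 77% |
| Main time test | 0.8 | 32% | 68% | 93% |
| Pooled contrast | 0.5 | 8% | 11% | 16% |
| Pooled contrast | 0.7 | 9% | 15% | 23% |
| Pooled contrast | 0.8 | 12% | 20% | 32% |

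**3. Evening baseline instead.** The means become (d, 0, d, 0, d, 0, d). The sum of squares is 4d² − 16d²/7 = 12d²/7, as before, and the pooled bias is −d/2. The rates are unchanged and only the direction reverses.

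**4. Clock-matched comparison.** Simulation (n = 15, r = 0.5, shifts of 0 to 0.8 SD) of morning sessions against a morning baseline gives no bias and about 5% false positives at every shift.

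**5. BAL versus NEG BAL.** In the same simulation, comparing the two phases on the same schedule gives no bias and about 5% at every shift.

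**The case against.** **A reader might infer that individual baseline-versus-session tests are badly inflated.** An uncorrected paired test at r = 0.7 would give 15%, 29% and 46% for the three shifts. The plan does not run that test. B5.8.2 allows post hoc paired t-tests only after a significant phase-by-time interaction, and then with Bonferroni correction. An equal diurnal shift in both phases creates no such interaction. Correction for six baseline comparisons alone brings the rates to about 4%, 9% and 19%, before the interaction requirement is applied. The uncorrected rates should not be used. The main time test is not subject to that requirement.

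**Session coding already separates morning from evening.** This is true, and a saw-tooth in the session means could be noticed. It would be wrong to say that every significant time effect will be read as a SUSOPS effect. But session coding does not supply the missing matched baseline, and coding by day or daily mean leaves half the shift in the contrast.

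**Vigilance might seem equally exposed.** For the wrist monitor the documents do not support that: B5.3, Ambulatory Vigilance and Sleep Evaluation, sets standardized times in baseline, SUSOPS and recovery. The point is confined to the computer battery, which includes the Psychomotor Vigilance Test.

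**A reader might infer that the study has only one baseline.** It has two, one before each SUSOPS. Each is a single session, so the mismatch remains within each period.

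**The size is wholly assumed.** This stands. The documents establish that the mismatch exists, not how large its effect is.

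**Conclusion.** The point holds for the computer mood/cognitive battery and for the before-versus-SUSOPS part of secondary hypothesis 4. One baseline session cannot match both daily test times, and the model names no factor to separate them. Ordinary diurnal change can therefore be mixed with a SUSOPS effect. Under the assumptions above, with r = 0.7, the main time test would be falsely significant in about 22% to 77% of trials if time means session, and a pooled contrast in about 9% to 23%. These figures illustrate sensitivity and do not estimate what will happen.

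The documents do not support extending this to the randomized diet comparison, which is unaffected when the two phases keep the same schedule. They also do not support extending it to the primary outcomes (IL-6, hepcidin, iron absorption) or to the wrist monitor. The change should be made because it is cheap and cannot be made after data collection, but the primary objectives do not depend on it.

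**What to change.** **B5.3, mood and cognitive assessments.** Define the pre-SUSOPS 1 baseline as the last two of the 4 to 5 sessions already planned, one in the morning and one in the evening, at the clock times used in SUSOPS. Hold the Recovery 1 baseline at one of those two times and state which. Optionally, add a second Recovery 1 session to make a pair there too. State also how the Recovery 1 session enters the analysis, since the assessment section names only the last pre-SUSOPS session.

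**B5.8.2.** For the battery, replace the undefined time within phase by day (baseline and SUSOPS days), time of day (morning, evening) and their interaction, alongside phase. Compare only clock-matched sessions with baseline. If Recovery 1 keeps a single session, only the matching half of the SUSOPS 2 sessions has its own period's baseline, and the plan should say so.

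**Cost.** The change is mainly to wording, plus scheduling one existing session at a set time. The optional Recovery 1 session takes about 55 min, the sum of the stated test times (5 + 5 + 10 + 5 + 5 + 15 + 10). The downside is practice: one of the paired baseline sessions follows one session less of practice, and only 2 to 3 sessions remain purely for familiarization. Those must be enough for stable performance, or a learning effect replaces the diurnal one.
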